6.3. Vital Signs and Physical Examination Findings

Vital Signs:

The following measurements will be analyzed:

- Systolic blood pressure (SBP) (mmHg)
- Diastolic blood pressure (DBP) (mmHg)
- Pulse Rate (beats per minute)
- Temperature [Axilla] (°C)
- Respiratory Rate (breaths per minute)

Baseline vital sign evaluations are defined as the last evaluation done before the study drug administration.

On-treatment evaluations will be those performed after the study drug administration to the completion of study/withdrawal date.

For vital signs parameters, normal range limits (indicators) are defined as follows:

Parameter	Unit	Normal range limits
SBP	mmHg	90 - 140
DBP	mmHg	60 - 90
Pulse Rate	beats per minute	50 - 100
Temperature	°C	36 - 38
Respiratory Rate	breaths per minute	12 - 20

For vital signs marked abnormal limits are defined as follows:

Abnormality Code	Vital Signs parameter		
	Pulse	DBP	SBP
	Abnormalities on actual values		
Abnormally low	≤45 bpm	≤50 mmHg	≤90 mmHg
Grade 1 or mild	-	> 90 mmHg - < 100 mmHg	>140 mmHg - < 160 mmHg
Grade 2 or moderate	-	≥100 mmHg - < 110 mmHg	≥160 mmHg - < 180 mmHg
Grade 3 or severe	-	≥110 mmHg	≥180 mmHg
Abnormally high	≥120bpm	-	-

The following analyses will be performed. Tables and figures:

- Descriptive statistics at each scheduled time point on actual value and changes from baseline. (Use the analysis time points defined in 2.1)
- Shift from pre- versus post-treatment cross-tabulations (with classes for low, normal, high ranges and using the analysis time points defined in 2.1)
- Tabulation of percentage of subjects with values beyond clinically important limits at each scheduled time point (Use the analysis time points defined in 2.1)
- Line plots of individual observed values at each scheduled time point (Use all the time points observed)
- Line plots of Mean and SD at each scheduled time point (Use the analysis time points defined in 2.1)

The following analyses will be performed. Listings:

- Listing of subjects with vital signs results
- Listing of subjects with any vital signs results outside the normal range
- Listing of subjects with any markedly abnormal vital sign results

Physical Examination:

Physical examination findings will be summarized at each scheduled at time point.

Baseline physical examination findings are defined as the last evaluation done before the study drug administration.

On-treatment evaluations will be those performed after the study drug administration to the completion of study/withdrawal date.

The following analysis will be performed. Tables:

- Tabulation of baseline and values at each scheduled time point (Use the analysis time points defined in 2.1)
- Shift from pre- versus post-treatment cross-tabulations and using the analysis time points defined in 2.1)

The following analyses will be performed. Listings:

- Listing of results (presence of abnormal findings) of physical examinations

6.4. ECG

Overall ECG interpretation will be summarized at each scheduled at time point.

Baseline 12-lead ECG evaluations are defined as the last evaluation done before the study drug administration.

On-treatment evaluations will be those performed after the study drug administration to the completion of study/withdrawal date.

The following analyses will be performed. Tables:

- Shift from pre- versus post-treatment cross-tabulations of overall ECG interpretation [Normal, Abnormal, Unevaluable]

The following analyses will be performed. Listings:

- Listing of overall ECG interpretation

6.5. Other Safety Parameters

Not applicable.

7. PHARMACOKINETICS/PHARMACODYNAMICS

7.1. Pharmacokinetics

Concentrations and PK parameters for DRV and COBI will be summarized. Concentrations will be also presented graphically. The parameters of interest and units are as follows (but not limited):

C_{\max}	ng/mL	Maximum plasma concentration
C_{last}	ng/mL	Concentration at last quantifiable time point
t_{\max}	h	Time to reach the maximum plasma concentration
AUC_{last}	h*ng/mL	Area under the plasma concentration-time curve from time zero to time the last quantifiable time, calculated by linear trapezoidal summation
λ_z	1/h	
Elimination rate constant associated with the terminal phase (including λ_z lower and λ_z upper). In the case the following criteria are not met, λ_z, AUC_{∞} and $t_{1/2, \text{term}}$ will be excluded from the descriptive statistics.
 
 The number of data points used for calculation of $\lambda_z \geq 3$. Adjusted coefficient of determination (R^2_{adj}) for the regression of $\lambda_z \geq 0.9000$. $t_{1/2, \text{term}} \times 1.5 < \lambda_z \text{ upper} - \lambda_z \text{ lower}$.
AUC_{∞}	h*ng/mL	
Area under the plasma concentration-time curve from time zero to infinite time. In the case following value ($\%AUC_{\infty, \text{ex}} > 20\%$), AUC_{∞} will be excluded from the descriptive statistics.
 $\%AUC_{\infty, \text{ex}} = \frac{AUC_{\infty} - AUC_{\text{last}}}{AUC_{\infty}} \times 100$
$t_{1/2, \text{term}}$	h	
Terminal elimination half-life.
 $t_{1/2, \text{term}} = \frac{\log_e 2}{\lambda_z}$
Vz/F	mL	Apparent volume of distribution at the terminal phase after extravascular administration
CL/F	mL/h	Apparent total body clearance of drug at the terminal phase after extravascular administration

Following rules will be applied for descriptive statistics.

- The plasma DRV and COBI concentrations collected outside the visit time window allowance will be excluded from the calculation of descriptive statistics.
- Below quantifiable limit (BQL) will be substituted with 0.
- The number subject displayed as "N" on summary tables will be the number of subject whose plasma concentrations are measured (include BQL) or PK parameters are calculated.
- When more than half (>50%) of plasma DRV and COBI concentrations are BQL at each scheduled time point, mean, median, and minimum will be shown as 'BQL', and SD, and %CV will be shown as 'NC' (not-calculated). If all plasma DRV and COBI concentrations are BQL, maximum will also be shown as 'BQL'. If a minimum concentration is substituted to '0', 'BQL' will be presented as minimum.
- When number of plasma DRV and COBI concentrations is equal to or less than 2, only N and mean will be calculated and SD, %CV, median, minimum and maximum will be shown as 'NC' regardless of the proportion of BQL.

Subjects will be excluded from the PK analysis if their data do not allow for accurate assessment of the PK (eg. incomplete administration of the study drug; subject vomited after receiving study drug; missing information of dosing and sampling times; concentration data not sufficient for PK parameter calculation).

Based on actual sampling times, PK parameters will be estimated using a non-compartmental analysis method with WinNonlin® (Version 6.4). The detail procedure is written in "[ATTACHMENTS](#)" of this document.

The following analyses will be performed. Tables and figures:

- Descriptive statistics of plasma DRV and COBI concentrations at each sampling time point (Use the analysis time points defined in [2.1](#))
- Descriptive statistics of PK parameters of DRV and COBI
- Line plots of arithmetic mean and SD of plasma DRV and COBI concentration time profiles (Use the analysis time points defined in [2.1](#))
- Line plots of arithmetic mean and SD of plasma DRV and COBI concentration time profiles with a log scale (values of 10^{-1} , 10^0 , 10^1 , 10^2 , 10^3 , 10^4) on the Y axis (Use the analysis time points defined in [2.1](#))
- Line plots of individual plasma DRV and COBI concentration time profiles (Use all the time points observed)
- Line plots of individual plasma DRV and COBI concentration time profiles with a log scale (values of 10^{-1} , 10^0 , 10^1 , 10^2 , 10^3 , 10^4) on the Y axis (Use all the time points observed)

The following analyses will be performed. Listings:

- Listing of individual plasma DRV and COBI concentrations at each sampling time point
- Listing of PK parameters of DRV and COBI

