***** End Mappings *****
```

- See the section that follows "Mappings" section in exported word file to check options.

```
Phoenix Build 6.4.0.768
Plasma Model
Title =
Linear Trapezoidal Linear Interpolation
Sparse = False
Dose Type = Extravascular
Dose Unit = mg
Weighting = Uniform Weighting; 0
Dose Normalization = None
Exclude Insufficient Profiles = False
Slope Settings
SUBJECT= [REDACTED] SUBSTANCE=DRV, Start Time=36, End Time=72, Exclusions=,
```

- See "Settings" section in exported word file to check subject level settings

```
WinNonlin 6.4
SUBJECT= [REDACTED], SUBSTANCE=DRV

Date: 2/21/2017
Time: 19:44:30

WINNONLIN NONCOMPARTMENTAL ANALYSIS PROGRAM
6.4.0.768
Core Version 04Jun2007

Settings
-----
Model: Plasma Data, Extravascular Administration
Number of nonmissing observations: 20
Dose time: 0.00
Dose amount: 800.00
Calculation method: Linear Trapezoidal with Linear Interpolation
Weighting for lambda_z calculations: Uniform weighting
Lambda_z method: Find best fit for lambda_z, Log regression

Summary Table
-----
Time      Conc.      Pred.      Residual      AUC      AUMC      Weight
h         ng/mL     ng/mL     ng/mL     h*ng/mL   h*h*ng/mL
-----
0.0000    0.0000
0.5000    37.90

```

Check lists for PK parameters***Overall settings***

Variable settings (See "Mappings" section in exported word file)		
Sort	SUBJECT, SUBSTANCE	
Carry	none	
Time	RELATIVE_ACT_TIME [h]	
Concentration	CONC [ng/mL]	
Dosing settings (See "Mappings" section in exported word file)		
Sort	SUBJECT, SUBSTANCE	
Dose	CONTAINS_DOSE [mg]	
Time of Dose	RELATIVE_ACT_TIME [h]	
Tau	none	
Options (See the section that follows "Mappings" section in exported word file)		
Model type	Plasma	
Calculation method	Linear Trapezoidal with Linear Interpolation	
Dose options type	Extravascular	
Dose unit	mg	
Weighting	Uniform weighting	

Checked all items 	Date:
	Signature:

Approval by CRO PaB Representative	Date:
	Signature:

Subject level settings

Subject ID	Dose time		Dose amount (DRV)		Dose amount (COBI)	
	0		800 mg		150 mg	

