	0		800 mg		150 mg	
	0		800 mg		150 mg	
	0		800 mg		150 mg	
	0		800 mg		150 mg	
	0		800 mg		150 mg	
	0		800 mg		150 mg	
	0		800 mg		150 mg	
	0		800 mg		150 mg	
	0		800 mg		150 mg	
	0		800 mg		150 mg	
	0		800 mg		150 mg	
	0		800 mg		150 mg	
	0		800 mg		150 mg	
	0		800 mg		150 mg	
	0		800 mg		150 mg	

Checked all items 	Date:
	Signature:

Approval by CRO PaB Representative	Date:
	Signature:

PK parameters to be used for this study

WinNonLin parameter name	WinNonLin's Definition	SDTM PPTEST	SDTM PPSTRESU	Note
AUC_%Extra_p_obs	Percentage of AUCINF_obs due to extrapolation from Tlast to infinity. $= \frac{AUCINF_{obs} - AUClast}{AUCINF_{obs}} \times 100$	AUC %Extrapolation Obs	%	Parameter to check validity of AUC.
AUCINF_obs	AUC from Dosing_time extrapolated to infinity, based on the last observed concentration (obs). $= AUClast + \frac{Clast}{\lambda z}$	AUC Infinity Obs	h*ng/mL	Written as "AUC _∞ " in clinical protocol.
AUClast	Area under the curve from the time of dosing (Dosing_time) to the last measurable (positive) concentration.	AUC to Last Nonzero Conc	h*ng/mL	Written as "AUClast" in clinical protocol.
Clast	Concentration corresponding to Tlast.	Last Nonzero Conc	ng/mL	Written as "Clast" in clinical protocol.
Cl_F_obs	Total body clearance for extravascular administration. = Dose/AUCINF_obs.	Total CL Obs by F	mL/h	

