Cmax	Maximum observed concentration, occurring at Tmax. If not unique, then the first maximum is used.	Max Conc	ng/mL	Written as "Cmax" in clinical protocol.
Dosing_time	Time of the last administered dose (assumed to be zero unless otherwise specified).			
HL_Lambda_z	Terminal half-life = $\ln(2) / \lambda_z$	Half-Life Lambda z	h	Written as "t _{1/2} " in clinical protocol.
Lambda_z	First order rate constant associated with the terminal (log-linear) portion of the curve. Estimated by linear regression of time vs. log concentration. If "No_points_lambda_z" < 3, Lambda_z is not be calculated by WinNonLin.	Lambda z	1/h	Written as " λ_z " in clinical protocol.
Lambda_z_lower	Lower limit on Time for values to be included in the calculation of λ_z .	Lambda z Lower Limit	h	Parameter to check validity of λ_z
Lambda_z_upper	Upper limit on Time for values to be included in the calculation of λ_z .	Lambda z Upper Limit	h	Parameter to check validity of λ_z .
No_points_lambda_z	Number of points used in the computation of λ_z . Time point for Cmax is excluded by WinNonLin.	Number of Points for Lambda z		Parameter to check validity of λ_z .
Rsq_adjusted	Goodness of fit statistic for the terminal elimination phase, adjusted for the number of points used in the estimation of λ_z .	R Squared Adjusted		Parameter to check validity of λ_z .
Tlast	Time of last measurable (positive) concentration.		h	

WinNonLin parameter name	WinNonLin's Definition	SDTM PPTEST	SDTM PPSTRESU	Note
Tmax	Time of maximum observed concentration. For non-steady-state data, the entire curve is considered. If the maximum observed concentration is not unique, then the first maximum is used.	Time of CMAX	h	Written as "t _{max} " in clinical protocol.
Vz_F_obs	Volume of distribution based on the terminal phase. Dose = $\frac{\text{Dose}}{\lambda z \times \text{AUCINF}_{\text{obs}}}$	Vz Obs by F	mL

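### CL/F and Vz/F have no exclusion rule of their own, although they are calculated from the λz and AUC∞ values that the SAP drops when the terminal fit fails

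*SAP*

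**What the plan says.** The parameter table in SAP 7.1 sets two exclusion rules.

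- **Terminal-fit rule (λz row).** Three conditions apply: at least 3 points, adjusted R² of at least 0.9000, and a regression window longer than 1.5 half-lives. If they are not met, λz, AUC∞ and t1/2,term "will be excluded from the descriptive statistics".
- **Extrapolation rule (AUC∞ row).** If more than 20% of AUC∞ is extrapolated, AUC∞ alone is left out.

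Vz/F and CL/F follow in the same table with a definition only. The CL/F entry, for example, reads "Apparent total body clearance of drug at the terminal phase after extravascular administration".

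The rules below the table cover sampling windows, values below the quantification limit, and N, which is "the number of subject whose plasma concentrations are measured (include BQL) or PK parameters are calculated". The planned output is "Descriptive statistics of PK parameters of DRV and COBI", with no exception stated.

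The parameter list in the SAP Attachment defines CL/F as "Total body clearance for extravascular administration. = Dose/AUCINF_obs". It describes Vz/F as "Volume of distribution based on the terminal phase", calculated as Dose/(λz × AUCINF_obs).

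**The concern.** CL/F is the reciprocal of AUC∞ scaled by dose, and Vz/F is CL/F divided by λz. If a λz is too poor to report, the Vz/F built on it is no better. The same holds for CL/F to the extent that AUC∞ relies on extrapolation. Because the rule names three parameters and stops, a programmer would reasonably keep the other two.

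Two things follow. The CL/F and Vz/F summaries would include values that fail the SAP's own quality test. They would also rest on a different set of subjects from AUC∞, so geometric mean CL/F would no longer equal Dose divided by geometric mean AUC∞ in the same report. With 6 to 8 subjects, one failed fit is enough to cause this, and whether to keep that subject would be decided after the data are seen.

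**Working it through.** **The plan's own figure.** SAP 1.4 gives 73% to 137% for n = 6, CV 40% and 90% confidence. On the log scale σ = √ln(1 + 0.40²) = 0.385, and the limits are exp(±t(0.95; 5) × 0.385/√6) = 72.8% to 137.3%. The figure reproduces. It is used below only as a yardstick.

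**Which criteria leave a gap.**
- *Fewer than 3 points:* no gap. The Attachment states "Lambda_z is not be calculated by WinNonLin" in that case, so AUC∞, CL/F and Vz/F do not exist either.
- *Adjusted R² or window length:* gap. λz is calculated and then excluded, while CL/F and Vz/F remain.
- *Extrapolation above 20%:* gap. AUC∞ is excluded, while CL/F and Vz/F remain.

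**How likely is a failure?** Protocol Table 1 gives mean (SD) half-lives of 6.7 (3.4) h for DRV and 3.8 (0.8) h for COBI. The window rule is met when 1.5 × t1/2 is less than the window length.
- Window 48–72 h (24 h): passes for t1/2 below 24/1.5 = 16 h. DRV mean + 2 SD is 6.7 + 6.8 = 13.5 h.
- Window 16–24 h (8 h), assuming the last quantifiable sample is at 24 h: fails for t1/2 of 8/1.5 = 5.33 h or more.
- Share of post-peak DRV AUC beyond 72 h, assuming mono-exponential decline from 4 h: 2^(-68/t1/2) = 0.09% at 6.7 h and 3.05% at 13.5 h.

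The example output in the Attachment shows the setting "Find best fit for lambda_z, Log regression", which should make a low adjusted R² less likely. The documents give neither the quantification limit nor a failure rate, so frequency cannot be computed.

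**Size of the effect of one affected subject (illustration).** Let fitted λz = true λz/k, with Clast taken as accurate and e the true extrapolated share. Then:
- reported extrapolation = ke/(1 + (k-1)e)
- CL/F ratio = 1/(1 + (k-1)e)
- Vz/F ratio = k/(1 + (k-1)e)
- shift in the geometric mean = ratio^(1/n) - 1

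Setting reported extrapolation to 20% gives e = 0.111 for k = 2 (λz at half its true value) and e = 0.333 for k = 0.5 (λz at twice its true value).

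| Case | Ratio | Shift, n = 6 | Shift, n = 8 |
|---|---|---|---|
| CL/F, k = 2 | 0.90 | -1.7% | -1.3% |
| CL/F, k = 0.5 | 1.20 | +3.1% | +2.3% |
| Vz/F, k = 2 | 1.80 | +10.3% | +7.6% |
| Vz/F, k = 0.5 | 0.60 | -8.2% | -6.2% |
| Vz/F, k = 2, e near 0 | 2.00 | +12.2% | +9.1% |
| Vz/F, k = 0.5, e near 0 | 0.50 | -10.9% | -8.3% |

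At e = 3% and n = 6, CL/F shifts by only -0.5% (k = 2) or +0.3% (k = 0.5).

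**Mismatch between tables.** This is a separate quantity. Suppose one subject is dropped for AUC∞ but kept for CL/F, and that subject's AUC∞ is f times the geometric mean of the others. Geometric mean CL/F then differs from Dose/geometric mean AUC∞ by a factor f^(-1/n). For n = 6 this is 1.12 at f = 0.5 and 0.89 at f = 2. It measures the difference in subject sets, not error in CL/F.

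**The case against.** The strongest reply is that other text already covers the case. Protocol 11.3 limits parameter calculation to subjects whose profiles permit it accurately, and SAP 7.1 excludes subjects whose data do not allow an accurate PK assessment, with open-ended examples. An analyst could rely on either to leave such values out. This stands in part, since there is some guidance. But neither clause sets an R², window or extrapolation test. The SAP clause also removes whole subjects, which would discard valid Cmax and AUClast, whereas the terminal-fit rule plainly works by parameter.

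Other points limit the weight of the concern and are accepted.
- The N rule is neutral. Read literally, it would also count the λz, AUC∞ and t1/2,term values that are expressly excluded.
- The 16–24 h window is an assumption and a minimum case. A 12–24 h window passes below 8 h and a 9–24 h window below 10 h. The Attachment's example output uses 36–72 h for DRV, which passes below 24 h. For COBI, 5.33 h is (5.33 - 3.8)/0.8 = 1.9 SD above the mean.
- Halving or doubling λz is arbitrary. Reported extrapolation of exactly 20% does not itself trigger the extrapolation rule, so the table illustrates an R² or window failure.
- The 73% to 137% precision is stated for Cmax and the two AUCs. It carries over to CL/F, which is the reciprocal of AUC∞ on the same log scale, but not to Vz/F.
- CL/F and Vz/F are not among the parameters named in Protocol 9.4.3, which only allows for additional ones. No hypothesis is tested, and individual values are listed.

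None of this supplies the missing rule. The SAP itself lists both parameters among those to be summarised.

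**Conclusion.** The concern holds, at minor severity. As written, SAP 7.1 keeps CL/F and Vz/F in the summary when the R², window or extrapolation rule has removed the quantities they are calculated from. Only the fewer-than-3-points case resolves itself.

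Under the stated assumptions (one affected subject, λz wrong by a factor of two), geometric mean Vz/F shifts by roughly 6% to 12% in either direction for n = 6 to 8. Geometric mean CL/F shifts by no more than about 3%. The CL/F shifts are small against the plan's precision. How often a fit would fail is unknown, and extrapolation above 20% is unlikely with sampling to 72 h. The results named in the protocol do not depend on CL/F or Vz/F.

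**What to change.** Make two edits in the SAP 7.1 parameter table.

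1. In the λz row, extend the list of excluded parameters to λz, AUC∞, t1/2,term, CL/F and Vz/F.
2. In the AUC∞ row, apply the 20% extrapolation rule to AUC∞, CL/F and Vz/F.

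Keep the individual values in the listing, with a flag for the criterion that failed.

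The cost is two phrases, with no new data and no change to sample size. CL/F and Vz/F may lose a subject, but only one already dropped for AUC∞. The tables would then rest on the same subjects, and geometric mean CL/F would again equal Dose divided by geometric mean AUC∞.

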7.2. Immune Response

Not applicable.

7.3. Pharmacodynamics

Not applicable.

7.4. Pharmacokinetic/Pharmacodynamic Relationships

Not applicable.

8. HEALTH ECONOMICS

[figure not shown]
Not applicable.

ATTACHMENTS

Procedure for non-compartment analysis using WinNonLin version 6.4

[figure not shown]
Starting a new project

- Right click and select "New" and "project" in "ObjectBrowser".

[figure not shown]

Loading data

[figure not shown]
- Right click "Data" and select "Import".

- Select NCA input file and open.

- Confirm following check boxes in "Data Import Wizard" and click "Finish and Open".

Setting unit

- Select variables and enter their units.
- "h" for RELATIVE_ACT_TIME
- "ng/mL" for CONC
- "mg" for CONTAINS_DOSE

Object Browser

New Project

Data

TMC114FD1HTX4002_Raw

Sheet1

File Edit Insert Send To Window Help

New Project >> Data >> TMC114FD1HTX4002 Raw (N)CA PD input yyyyymmdd >> Sheet1

	PERIOD	DAY	RELATIVE_NOMINAL_TIME	SCHED_TIME	TIME	RELATIVE_ACT_TIME (h)
1	1	1		0 PREDOSE	-0.7	0
2	1	1		0.5 30min	0.5	0.5
3	1	1		1 1h	1	1
4	1	1			1.5	1.5
5	1	1			2	2
6	1	1		2.5 2h30min	2.5	2.5
7	1	1		3 3h	3	3
8	1	1		3.5 3h30min	3.5	3.5
9	1	1		4 4h	4	4
				4.5 4h30min	4.5	4.5

Columns

TIME
RELATIVE_ACT_TIME
ACTTIM_UNIT
ACT_TIMD
SUBSTANCE
SPECIMEN
MATRIX

Add Remove

Data Type: Numeric
Unit: h

Display Format

Custom G8

Numeric Required Decimals Optional Decimals

[figure not shown]
Use Thousands Separator

Properties Information History

Ready

[figure not shown]
Model

- Right click spread sheet name and select settings as shown below.

Variables

[figure not shown]
- Select "Main" in "Setup" tab and identify how input variables are used.
- SUBJECT and SUBSTANCE: Sort
- RELATIVE_ACT_TIME: Time
- CONC: Concentration
- Other: None

Select variables and radio button.

[figure not shown]
Options

- Confirm following settings.
- Model Type: Plasma (200-202)
- Weighting: Uniform
- Calculation Method: Linear Trapezoidal Linear Interpolation
- Dose Options Type: Extravascular

[figure not shown]

Dosing

- Select "Dosing" in "Setup" tab.
- Click "Select source" button and open "Select Source" dialog.

[figure not shown]

- Click spread sheet name.

- Identify how input variables are used.
- SUBJECT and SUBSTANCE: Sort
- CONTAINS_DOSE: Dose
- RELATIVE_ACT_TIME: Time of Dose
- Other: None

[figure not shown]
Select variables and radio button.

Execution

[figure not shown]
- Click "Execute NCA" button.

"Execute NCA" button

[figure not shown]

Saving analysis results

[figure not shown]
- Right click "Final Parameters" in "Results" tab and select "Export".

[figure not shown]
- Save as "ncaoutput.csv".

[figure not shown]
- Confirm following check box in "Data Export Options" and click "OK".

[figure not shown]
- Left click "File" and select "Word Export".

- Select items as shown below and click "Export" button in "Word Export" dialog.

- Click "OK".

- Save created word file as "xxxx.doc".

Quality control of PK parameters

- Confirm all items that listed on the check list.
- See "Mappings" section in exported word file to check variable and dosing settings.

```
